7.2 Statistical analyses

Trial data collected from both countries will be stored in secure study databases before being merged and analysed by the study statistician at NIHI. Statistical analysis will be performed using SAS version 9.4 (SAS Institute Inc., Cary, NC, USA).

Data analyses will be carried out on an intention-to-treat (ITT) basis. All 150 randomised companies will be included in the primary ITT analysis. A per-protocol (PP) analysis will also be conducted including only those intervention companies who participate in the intervention programme, defined in this instance as agreement to participate in the programme and attendance at minimum one meeting regarding the intervention. A statistical analysis plan prepared by the study statistician (and agreed upon by the Steering Committee) will be prepared a priori. The CONSORT 2010 statement (33) with extension to cluster randomised trials guidelines will be followed when reporting the main trial results.

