A total of 150 companies (intervention n=100, control n=50) across both countries, with a minimum of 10 products per company, will provide 90% power at a 5% level of significance to detect a minimum 0.48-unit difference between groups in the mean HSR of all packaged food products over the 24-month follow-up period, assuming a mean HSR of products of 2.95, a standard deviation (SD) of 1.25, and an intra-cluster correlation (ICC) between products produced by the same company of 0.4. This would constitute an approximate 16% increase in the star rating (healthiness) of foods produced by the intervention companies compared to foods produced by the control group companies.

We estimate that about half of the intervention companies will participate in the intervention programme, which will reduce the effective sample size. A total of 100 companies (50 intervention and 50 control companies) will provide 80% power to detect the expected effect size on the primary outcome under the same assumptions.

Statistical analysis

Trial analyses will be conducted on an intention-to-treat (ITT) basis, following the CONSORT 2010 statement guidance with extension to cluster randomised trials. All randomised companies will be included in the primary ITT analysis. A per-protocol (PP)

analysis will also be conducted including only those intervention companies that participate in the intervention programme as per protocol.

Descriptive information will be presented at both company and food category level by treatment group pre- and post-intervention. Primary and secondary efficacy outcomes will be tested between intervention and control groups using generalised linear mixed models. The fixed effects will include treatment group, stratification factors, baseline outcome value and key food categories. Food company will be included as a random cluster effect. The ICC coefficients will be estimated using the trial data. The size of any intervention effect will be estimated overall and by key food categories. Country-level analysis will also be undertaken.

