7.1 Sample size

A total of 150 food companies across both countries (intervention n=100, control n=50) will provide 90% power at a 5% level of significance to detect a minimum 0.48-unit difference between two randomised groups in the mean HSR of all packaged food and beverage products at the end of intervention, assuming a mean HSR of products of 2.95, a standard deviation (SD) of 1.25, and an intra-cluster correlation (ICC) between products produced by the same company of 0.4. This effect size would constitute an approximate 16% increase in the star rating (healthiness) of foods produced by the intervention companies compared to the foods produced by the control group companies.

We estimate that about half of the intervention companies will participate in the intervention programme, which will reduce the effective sample size. A total of 100 companies (50 intervention and 50 control companies) will provide 80% power to detect the expected effect size on the primary outcome under the same assumptions.

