7.2.1 Baseline characteristics

Baseline data collated for all randomised companies will include:

- Company demographics and information (company name, key brands, product categories, category market share, category sales revenue, head office location)
- Baseline product portfolio information (number of products, average nutrient content per 100g (energy, saturated fat, sodium, total sugar, fibre etc.), mean estimated HSR, % products displaying HSR or other nutrition label)

Data collected at both company and food category level will be summarised descriptively by treatment group. Continuous variables will be presented as numbers of observations, means, standard deviations (SD), medians and ranges. Categorical variables will be presented as frequencies and percentages. Simple tests comparing two groups at baseline will not be undertaken as per the CONSORT guidelines. Such tests also do not consider the clustered nature of the data in a cluster randomised trial.

7.2.2 *Intervention effects*

All food companies will be included in the group they were allocated to, in order to determine the effects of the provision of tailored support to food companies on their nutrition-related policies and practices, compared to no intervention. Both primary and secondary efficacy outcomes will be tested between intervention and control groups using generalised linear mixed models. The fixed effects will include treatment group, stratification factors, baseline outcome values, and key food categories. Food company will be included as a random cluster effect. The size of any intervention effect will be estimated overall and by key food categories. Model-adjusted group differences will be reported with 95% confidence intervals and p-values, and the ICC coefficients will be estimated. Statistical tests will be two-sided at a 5% significance level.

Pre-specified subgroup analysis will be conducted for each country separately. A secondary analysis will examine only products available over the full duration of the intervention period.

7.2.3 *Economic analyses*

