Resource use associated with the co-production components of the intervention and collected from intervention companies will be assumed to represent the incremental costs for the intervention. At 24 months post intervention, the control companies will also be asked (during the process evaluation in-depth interviews and questionnaire) about relevant actions taken to improve nutrition related policies and practices over the last 24 months and associated resource use. Resource use data analysis will be completed on an ITT basis and complemented with a per protocol (PP) analysis. These will be reported as the numbers of observations, means, standard deviations (SD), medians and ranges. Both the within-trial and modelled cost-effectiveness analyses will use the treatment effects reported using the ITT and PP analyses. Any uncertainty associated with resource use and treatment effects will be accounted for using Monte-Carlo simulations (using the Microsoft Excel add-in Ersatz (34)) and all results will be presented with 95% uncertainty intervals. A detailed economic evaluation protocol will be developed and agreed upon by the Steering Committee.

7.2.4 *Procedures to account for missing data*

We do not anticipate missing data for the primary outcome, which will be measured independently using the Australasian Health Star Rating (HSR) nutrient profiling system applied to the foods and beverages produced and sold by the food companies included in the study. The nutrient data to estimate HSR will be extracted from the New Zealand Nutritrack and Australian FoodSwitch databases directly, both of which contain annually updated Nutrition Information Panel values, ingredients, and labelling information for packaged products available for sale in major supermarket stores in each country.

Generalised linear mixed models will also take into account any missing data at the product level using maximum likelihood methods, assuming they are missing at random.

Missing resource use data will be handled using various methods and guided by the most likely mechanism for missing data (e.g., data missing at random, covariate dependent missing etc.) (35).

7.2.5 *Interim analyses*

No interim analysis will be undertaken during the trial. All analyses will be conducted following completion of the 24-month intervention period.

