Data from completed surveys will be manually entered by the research team into a data entry programme. Data entry personnel will be identified from the members of the research team, and will be trained if necessary. Completed survey questionnaires will be checked by a member of the research team before data entry starts. Any identifying information other than the participant ID number will be detached from questionnaires and the data entry program will keep confidential information in a separate file if entered. Responses will remain linked to the allocated participant ID. Data entry will be done by another member of the research team using a data entry program (i.e. REDCap). The data entry program (e.g., REDCap) is only accessible to the responsible research team members and to no one else. This is essential for the confidentiality of data. Another member of the research team will check entered data for the purpose of identifying typing errors, missing values, and overall quality of data entry. Following survey data entry completion, raw data will be extracted from REDCap as a .csv file for analysis and storage, and then deleted from the data entry programme.

In person or virtual (e.g., Zoom) interviews will be audio and video recorded. Audio files will be transcribed verbatim by the research team. Identifiable audio files and transcripts will be preserved for the minimum required period (see below). De-identified data only will be reported in any publicly available research outputs.

7.3.5 *Economic evaluation*

Resource use data collection tools will be developed in Microsoft Excel to capture the costs related to the implementation of the intervention. This data will be captured monthly by the study project managers and relevant study invoices. Resource use questionnaires will be developed in Excel to collect data tailored to the actions being taken by the intervention companies and will be collected at each of the six intervention sessions. A more detailed resource use questionnaire will be developed in Qualtrics and collected at 12 months and 24 months.

All study data will be stored and backed-up securely at The University of Auckland or Deakin University as appropriate (on a password protected share drive). Paper-based data will be stored in a locked filing cabinet. Only members of the research team will have access to the stored data. All reports from the study will be written in a way such that no individual companies can be identified.

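### The secondary per-protocol analysis compares self-selected participants with, by implication, all controls, and this non-randomised estimate enters the cost-effectiveness analyses alongside ITT

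*Protocol*

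**What the plan says.** - **Analysis sets (Protocol 7.2).** ITT on all 150 randomised companies is primary. In addition, "A per-protocol (PP) analysis will also be conducted including only those intervention companies who participate in the intervention programme". A company counts as participating if it agrees to take part and attends at least one meeting.
- **Uptake (1 and 7.1).** About half of the intervention companies are expected to participate. An 80% power figure is then given for 50 intervention against 50 control companies.
- **How participation arises (6.3, 7.4.3).** Engagement is voluntary and follows an invitation sent after allocation. Control companies are left alone during the intervention phase and are first asked for information at 24 months.
- **Motivation (6.11, and Table 1 in 6.12).** Prioritisation and motivation for change are surveyed at baseline in intervention companies only. Controls are surveyed only at 24 months.
- **Model (7.2.2).** Fixed effects are treatment, stratification factors, baseline outcome and key food categories, with company as a random effect. "Statistical tests will be two-sided at a 5% significance level".
- **Economics (7.2.3).** "Both the within-trial and modelled cost-effectiveness analyses will use the treatment effects reported using the ITT and PP analyses". Resource use is likewise analysed by ITT and by PP.
- **Condition on the economics (1, statistical methods).** The economic evaluation is done if the intervention succeeds in changing the primary outcome. Otherwise only a costing analysis is done.

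**The concern.** The PP rule removes companies from one arm only, and it does so on a choice made after allocation. Companies that accept an offer of nutrition support may differ from those that decline in how much they would have reformulated anyway. The control arm contains both kinds and they cannot be told apart, because no control receives the offer. The PP difference therefore combines any programme effect with the difference between accepters and the average company.

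The planned covariates help only in part. Baseline HSR, strata and food category capture where a company starts and what it makes. They do not capture its readiness to change, and that cannot be added as a covariate in this contrast because it is not measured at baseline in controls.

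Two uses of the PP estimate are at stake. One is its natural reading as the effect of actually taking part. The other is its role as a second treatment effect in both the within-trial and the modelled cost-effectiveness analyses.

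**Working it through.** **Inputs from the protocol (1 and 7.1).** SD of HSR 1.25; ICC "between products produced by the same company of 0.4"; cluster size "with a minimum of 10 products per company"; two-sided 5% test; target difference 0.48; 100 against 50 companies; expected uptake 50%.

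**Input not in the protocol.** The gap g: the difference in untreated 24-month company mean HSR between would-be participants and decliners, after adjustment. I show 0.1 to 0.4 stars. This is an assumption.

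**Step 1: reproduce the plan's power.**
- Design effect = 1 + (10 - 1) x 0.4 = 4.6.
- SD of a company mean = 1.25 x sqrt(4.6/10) = 0.848.
- 100 against 50: SE = 0.848 x sqrt(1/100 + 1/50) = 0.147, and power at 0.48 is 90.5% (90.1% by noncentral t). Stated: 90%.
- 50 against 50: SE = 0.848 x sqrt(2/50) = 0.170, and power at 0.48 is 80.8% (80.0% by noncentral t). Stated: 80%.

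Both figures reproduce. The 80% figure has the shape of the PP contrast: 50 participants against all 50 controls, at the full 0.48.

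**Step 2: expected values.** Let p be uptake, tau the effect in participants, and M_P and M_D the untreated means of would-be participants and decliners, with g = M_P - M_D. Assume the invitation alone does nothing.
- Control mean = p M_P + (1 - p) M_D.
- PP difference = M_P + tau - [p M_P + (1 - p) M_D] = tau + (1 - p) g.
- ITT difference = p tau.
- Complier-average effect = ITT difference / p = tau.

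The PP bias is (1 - p) g, which is 0.5 g here. Its sign is the sign of g.

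**Step 3: size under a true null.** Rejection rate = P(|Z + bias/SE| > 1.96), with the unadjusted SE of 0.170.

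| Assumed g | PP bias | PP rejection rate |
|---|---|---|
| 0.1 | 0.05 | 6.0% |
| 0.2 | 0.10 | 9.1% |
| 0.3 | 0.15 | 14.3% |
| 0.4 | 0.20 | 21.8% |

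A simulation of 20,000 trials per setting agrees. At g = 0.2 the PP rejection rate was 9.4%, and at g = 0.4 it was 23.3%. ITT rejection stayed at 5.1 to 5.3%. A negative g of the same size gives the same rejection rates with the estimate on the wrong side of zero. If baseline adjustment shrinks the SE and leaves the residual gap unchanged, these rates rise. If it also shrinks the gap, they may not.

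**Step 4: size when participants benefit by 0.48.** The PP expectation is 0.48 + 0.5 g: 0.58 at g = 0.2 and 0.68 at g = 0.4 (simulated 0.578 and 0.679). The simulated complier-average estimate averaged 0.476 and 0.475. With g negative, PP would average 0.38 and 0.28.

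**Step 5: what ITT shows in that case.** The expected ITT difference is 0.5 x 0.48 = 0.24, and power with 100 against 50 is about 37%.

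**Step 6: precision of the alternative.** The SE of the complier-average effect is about 0.147/0.5 = 0.294, against 0.170 for PP, a ratio of 1.73.

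**The case against.** **PP is secondary.** ITT is primary and no decision rule rests on PP. This stands. A reader might infer that the trial's main efficacy conclusion is compromised. It is not.

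**The economic evaluation is gated.** A reader might infer that PP could produce favourable cost-effectiveness results for a programme that does nothing. The condition in section 1 largely blocks this: if success means a significant ITT result, then under a true null the evaluation runs only after a false-positive ITT finding, about 5% of the time. The protocol does not say in terms which analysis defines success, but the primary one is ITT. What remains is a biased PP effect reported beside a positive ITT effect.

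**The direction and size of the gap are unknown.** This stands. Keen companies may accept, but so may companies with few nutrition resources, so PP could be too low. Larger false-positive rates than those above need a gap close to or above the 0.48 that the whole programme is powered to detect, or an assumed baseline correlation that the protocol does not give. The documents support neither.

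**The one-meeting threshold looks lax.** Section 7.3.5 says resource-use questionnaires "will be collected at each of the six intervention sessions", so one meeting may seem too little to count as participation. For a complier-average estimate, however, a low threshold is the safer choice, because it keeps partly exposed companies out of the non-participant group. It is not a defect here.

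**Details may be settled in the SAP or the economic evaluation protocol.** In part. That the PP comparator is every control is inferred, not stated. But the one-sided restriction and the use of the PP effect in the economics are both fixed in this protocol, and no matching restriction on controls is possible.

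**Conclusion.** The point holds for a secondary analysis. As defined, PP is a non-randomised contrast with bias (1 - uptake) times the untreated gap, in either direction, and the planned covariates cannot fully remove it. At 50% uptake and assumed gaps of 0.1 to 0.4 stars, that is 0.05 to 0.20 stars, with a PP false-positive rate of about 6 to 22% at the unadjusted SE. The protocol gives no value for the gap, so these figures illustrate scale and do not predict the result. The formula does not depend on them. The algebra also assumes that the comparator is all controls and that an invitation without participation has no effect.

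The choice still deserves correction. If only participants benefit, ITT is expected to show half their effect, so the PP figure could easily be the more striking of the two, and section 7.2.3 already commits it to both cost-effectiveness analyses.

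**What to change.** 1. In section 7.2, add a complier-average causal effect as the estimate of the effect of taking part. Use random allocation as the instrument for participation as already defined there, with company-level inference: a two-stage model, or the ITT difference divided by uptake with a bootstrap over companies. Controls are not offered the programme, so non-compliance is essentially one-sided.
2. Keep PP if wanted, labelled as exploratory and non-randomised.
3. In section 7.2.3, make the ITT effect the economic base case. Use the complier-average effect, with matching participant costs, as the scenario in place of PP.

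**Cost.** Some wording and one extra model. Allocation, participation and outcome are already collected.

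**Limits.** The estimate needs the exclusion restriction that a bare invitation changes nothing. Its interval is wider than that of PP (SE about 0.29 against 0.17), and it adds essentially no power beyond the ITT test. If programme costs fall mainly on participants, its cost per unit change in HSR will be close to the ITT ratio, because cost and effect scale together.

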7.2.1 Baseline characteristics

Baseline data collated for all randomised companies will include:

- Company demographics and information (company name, key brands, product categories, category market share, category sales revenue, head office location)
- Baseline product portfolio information (number of products, average nutrient content per 100g (energy, saturated fat, sodium, total sugar, fibre etc.), mean estimated HSR, % products displaying HSR or other nutrition label)

Data collected at both company and food category level will be summarised descriptively by treatment group. Continuous variables will be presented as numbers of observations, means, standard deviations (SD), medians and ranges. Categorical variables will be presented as frequencies and percentages. Simple tests comparing two groups at baseline will not be undertaken as per the CONSORT guidelines. Such tests also do not consider the clustered nature of the data in a cluster randomised trial.

7.2.2 *Intervention effects*

All food companies will be included in the group they were allocated to, in order to determine the effects of the provision of tailored support to food companies on their nutrition-related policies and practices, compared to no intervention. Both primary and secondary efficacy outcomes will be tested between intervention and control groups using generalised linear mixed models. The fixed effects will include treatment group, stratification factors, baseline outcome values, and key food categories. Food company will be included as a random cluster effect. The size of any intervention effect will be estimated overall and by key food categories. Model-adjusted group differences will be reported with 95% confidence intervals and p-values, and the ICC coefficients will be estimated. Statistical tests will be two-sided at a 5% significance level.

Pre-specified subgroup analysis will be conducted for each country separately. A secondary analysis will examine only products available over the full duration of the intervention period.

7.2.3 *Economic analyses*

Resource use associated with the co-production components of the intervention and collected from intervention companies will be assumed to represent the incremental costs for the intervention. At 24 months post intervention, the control companies will also be asked (during the process evaluation in-depth interviews and questionnaire) about relevant actions taken to improve nutrition related policies and practices over the last 24 months and associated resource use. Resource use data analysis will be completed on an ITT basis and complemented with a per protocol (PP) analysis. These will be reported as the numbers of observations, means, standard deviations (SD), medians and ranges. Both the within-trial and modelled cost-effectiveness analyses will use the treatment effects reported using the ITT and PP analyses. Any uncertainty associated with resource use and treatment effects will be accounted for using Monte-Carlo simulations (using the Microsoft Excel add-in Ersatz (34)) and all results will be presented with 95% uncertainty intervals. A detailed economic evaluation protocol will be developed and agreed upon by the Steering Committee.

7.2.4 *Procedures to account for missing data*

We do not anticipate missing data for the primary outcome, which will be measured independently using the Australasian Health Star Rating (HSR) nutrient profiling system applied to the foods and beverages produced and sold by the food companies included in the study. The nutrient data to estimate HSR will be extracted from the New Zealand Nutritrack and Australian FoodSwitch databases directly, both of which contain annually updated Nutrition Information Panel values, ingredients, and labelling information for packaged products available for sale in major supermarket stores in each country.

Generalised linear mixed models will also take into account any missing data at the product level using maximum likelihood methods, assuming they are missing at random.

Missing resource use data will be handled using various methods and guided by the most likely mechanism for missing data (e.g., data missing at random, covariate dependent missing etc.) (35).

7.2.5 *Interim analyses*

No interim analysis will be undertaken during the trial. All analyses will be conducted following completion of the 24-month intervention period.

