6.12 Schedule of intervention and follow-up

Companies will be approached in the first half of 2021 and the intervention will start from Q2 or Q3 2021, and will run for 12 months.

Trial assessments will be undertaken at baseline, and at 12 months and 24 months post-baseline [Table 1].

In New Zealand, the 2019 Nutritrack dataset will be used for baseline assessment of the primary outcome, and the 2022 and 2023 datasets (collected Q1/2 each year) will be used for the 12-month and 24-month primary outcome assessments. In Australia, the 2019 FoodSwitch dataset will also be used for baseline assessment of the primary outcome, and the 2021 and 2022 datasets (collected Q4 each year) will be used for the 12-month and 24-month primary outcome assessments. Data collection was disrupted in both countries in 2020 due to COVID-19, and thus the 2019 datasets were selected for use as a baseline.

Table 1: Details of follow-up

Timing		0 weeks (2021)	12 months (2022)	24 months (2023)
Description	Screening + Engagement (intervention companies only)	Baseline data collection + Randomisation (all companies)	Interim follow-up (all companies)	Final follow-up (all companies)
Approach to intervention company				
Obtain intervention company representative contact details	✓			
Send introductory email and follow-up to seek engagement	✓			
Confirm engagement with programme	✓			
Company description				
Company demographics		✓		
Product portfolio information		✓		
Outcome assessments				
Nutrient profile of company product portfolio (mean Health Star Rating)		✓ (2019 datasets)	✓ (2022 dataset NZ, 2021 dataset Aus)	✓ (2023 dataset NZ, 2022 dataset Aus)
Nutrient content (including sodium, sugar, and saturated fat) of the foods and beverages		✓	✓	✓
% products displaying HSR		✓		✓
Nutrition-related policy and commitment scores (BIA-Obesity assessment)		✓		✓
Level of company prioritization and motivation for change; enablers and barriers		✓ (intervention companies only)		✓
Resources associated with intervention and relevant actions undertaken by control companies			✓ (resource use data for intervention company actions collected over the 12 months of the intervention)	✓

7. Statistical Considerations

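### Section 7.2.2 plans a separate analysis in each country and names no treatment-by-country interaction, so as written the plan yields two country results and no test of whether they differ

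*Protocol*

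**What the plan says.** Section 7.2.2 (Intervention effects) says: "Pre-specified subgroup analysis will be conducted for each country separately". The overview adds only that a country-level analysis will be done. The mixed model in 7.2.2 has fixed effects for arm, the randomisation strata (country is one), the outcome at baseline and food category, with company as a random effect. It lists no product of arm with country or with category. The protocol names no interaction or heterogeneity test in any section.

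The same section says of food categories: "The size of any intervention effect will be estimated overall and by key food categories". It then says in general terms that adjusted group differences come with 95% CIs and p-values, and: "Statistical tests will be two-sided at a 5% significance level".

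Section 7.2 refers to a statistical analysis plan to be written a priori, which is not at hand.

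Section 6.12 sets different follow-up waves by country. For Australia, "the 2021 and 2022 datasets (collected Q4 each year) will be used for the 12-month and 24-month primary outcome assessments". New Zealand uses its 2022 and 2023 datasets, collected in the first half of each year. The intervention starts in the second or third quarter of 2021 in both.

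**The concern.** Two within-country tests each ask whether there is an effect in that country. Neither asks whether the effect differs. If one p-value falls below 0.05 and the other does not, the natural reading is that the programme worked in one country and not in the other. That pattern can easily arise when the effects are identical, because each country holds only part of the sample.

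The audience makes this reading likely. Section 11.5 sends the findings to health authorities in New Zealand and, separately, to those in Australia, and each will look for its own result. The primary pooled analysis is not affected. What is at stake is the interpretation of a pre-specified subgroup result.

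**Working it through.** **Inputs from the protocol.** Sections 1 and 7.1 give "a standard deviation (SD) of 1.25", "an intra-cluster correlation (ICC) between products produced by the same company of 0.4" and, for cluster size, "with a minimum of 10 products per company". There are 100 intervention and 50 control companies, allocated 2:1 within country strata, and tests are two-sided at 5%.

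**Assumptions.** The protocol does not give the country split, so the larger country is taken to hold 50% to 75% of companies. As in the protocol's own calculation, no gain from baseline adjustment is assumed. Normal approximations are used throughout.

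**Step 1: reproduce the stated power.** Section 7.1 says 150 companies "will provide 90% power at a 5% level of significance to detect a minimum 0.48-unit difference between two randomised groups".

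- Variance of a company mean = 1.25² × (0.4 + 0.6/10) = 0.719, so its SD is 0.848.
- 100 v 50: SE = √(0.719 × (1/100 + 1/50)) = 0.147. Power = Φ(0.48/0.147 − 1.96) = 90.5% (stated 90%).
- 50 v 50: SE = √(0.719 × 2/50) = 0.170. Power = 80.8% (stated 80%).

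Both figures reproduce.

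**Step 2: same inputs within a country.** With 75 companies per country (50:25), SE = √(0.719 × (1/50 + 1/25)) = 0.208. Power at 0.48 = Φ(0.48/0.208 − 1.96) = 64%.

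**Step 3: chance that exactly one country is significant.** With country powers a and b, this is a(1 − b) + b(1 − a). At 50:50 and a common effect of 0.48 it is 2 × 0.637 × 0.363 = 46%.

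| Country split | Power in each, effect 0.48 | Exactly one significant, 0.48 | Exactly one significant, 0.24 |
|---|---|---|---|
| 50:50 | 64%, 64% | 46% | 33% |
| 60:40 | 72%, 54% | 48% | 34% |
| 67:33 | 76%, 47% | 51% | 34% |
| 75:25 | 81%, 37% | 58% | 35% |

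The 0.24 column is an illustration: the target effect halved, in line with the protocol's expectation that about half the intervention companies take part. With no effect in either country the figure is 2 × 0.05 × 0.95 = 9.5%.

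**Step 4: sensitivity to baseline adjustment.** Section 7.2.2 adjusts for baseline. If the baseline and follow-up company means correlated at 0.8 (an assumption), the SE at 50:50 would fall to 0.208 × √(1 − 0.64) = 0.125. Power at 0.48 would be about 97% and exactly one country would be significant in about 6% of trials. At 0.24, power would be about 49% and the figure about 50%.

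**Step 5: what an interaction test offers.** Without baseline adjustment, the SE of the country difference is √(SE₁² + SE₂²) = 0.294 at 50:50 and 0.339 at 75:25. Power for a true between-country difference of 0.48 is Φ(0.48/0.294 − 1.96) = 37% and Φ(0.48/0.339 − 1.96) = 29%. The difference detectable with 80% power is 2.80 × SE = 0.82 to 0.95 stars. When the effects are equal, the test wrongly signals a difference in 5% of trials at any split.

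**The case against.** Several objections have force.

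- **Silence is not exclusion.** A reader might infer that the protocol rejects an interaction test. It does not: it never mentions one, and the analysis plan could add it. It also nowhere says that the two country p-values will be compared. What stands is narrower: the protocol does fix one method, separate analyses, and that method alone cannot answer whether the countries differ.
- **Separate estimates are legitimate.** Randomisation is stratified by country, so each within-country comparison is a valid randomised comparison. The two databases also differ in stores and collection months, which could justify letting other coefficients vary by country. Neither point removes the need for an estimate of the difference.
- **The 46% to 58% is conditional.** It needs a real common effect of 0.48, an assumed split and no gain from baseline adjustment. A reader might infer that conflicting country results are the usual outcome. The documents do not support that: the range runs from about 6% to 58% depending on inputs they do not give.
- **Discordance is not a type I error.** The 46% and the 5% measure different things. The interaction test would miss a true 0.48 difference in 63% to 71% of trials, so it brings its own risk of misreading.
- **Food categories.** A reader might infer that a p-value is planned for each category, and compute a family-wise error over the 15 Nutritrack food groups. The text says only that effects will be estimated by category. The p-value sentence is general, the number of key categories is not given, and an estimate by category could itself come from an interaction term. No multiplicity figure can be drawn from this.

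**Conclusion.** The point holds in limited form. Section 7.2.2 commits to separate country analyses with a main-effects model and names no test of whether the effect differs. On the protocol's own sample size inputs and a split of 50:50 to 75:25, an identical 0.48 effect would be significant in exactly one country in about 46% to 58% of trials. The figure is about 33% to 35% at 0.24 and about 10% with no effect. Strong baseline adjustment would lower it at 0.48, but not necessarily at a smaller effect.

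The primary analysis is untouched, and harm arises only if the two country p-values are set against each other.

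The differing follow-up dates are a separate matter of interpretation. The final wave is Q4 2022 in Australia and Q1/2 2023 in New Zealand, one to two quarters later. A reader might infer that an interaction term would deal with this. It would not, since the interaction estimate carries the same mixture of country and follow-up time.

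**What to change.** In section 7.2.2 or the analysis plan, replace the country sentence with text to this effect: country differences will be assessed by a treatment-by-country interaction in the primary mixed model, reported as one estimate with its 95% CI and p-value. Country-specific effects and 95% CIs will be taken from that model and treated as descriptive. No country difference will be claimed from separate p-values.

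Add three short statements:

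- Power of the interaction is low (about 29% to 37% for a 0.48 difference, with 0.82 to 0.95 stars detectable at 80%, before any gain from baseline adjustment), so a non-significant result does not show equal effects.
- The country contrast also reflects different follow-up dates.
- If effects by food category are tested, a treatment-by-category term will be used in the same way.

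The cost is a few sentences and one model term. Country is already in the model as a stratification factor, and no new data are needed. The drawback is the imprecision of the interaction estimate, which separate analyses would leave out of sight rather than avoid.
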